8.4.2 Parameters Collected during Pre-Dose Evaluation in Part II

In Part II the pre-dose assessment is done in every cycle for the 1 -year treatment period if not otherwise stated. Pre-Dose assessments maybe taken also up to three days before the Day 1 in each cycle.

- Height (only in Cycle 1)
- Weight
- Vital signs (blood pressure, heart rate, body temperature and respiratory rate).
- A targeted physical examination covering the major body systems (e.g. general appearance, head [ear, nose and throat], cardiovascular, eyes, respiratory, abdomen, urogenital, musculoskeletal, neurological, lymph nodes and skin)
- ECG (in Cycles 1, 2, 4, 6, and every second cycle thereafter; the ECG must be performed also always if clinically indicated)
- ECOG performance status
- Urine dipstick test
- PK sampling (only in Cycles 1, 2, 3 and 4)
- ADA sampling (on Cycles 1, 2, 4, 6, and every second cycle thereafter, or if clinically indicated)
- Blood samples
 - CBC
 - CMP
 - Endocrine panel (cortisol, lipase, pancreas-specific amylase , thyroid stimulating hormone, PTH, free thyroxine (T4), free triiodothyronine (T3), troponin)
 - Hepatitis B and C virus (quantitative assessment in Cycles 1, 2, 4 and 6 if tested initially positive)
 - LDH
 - LDL Cholesterol
 - AFP (HCC subjects)
 - CRP
 - CA-125 (OC subjects)
 - CA19-9 (PDAC, gallbladder cancer, cholangiocarcinoma, gastric adenocarcinoma subjects)
 - CEA (CRC, ER+ BC, gastric adenocarcinoma subjects)
 - CA-15-3 (ER+ BC subjects)
- Research blood samples
 - At selected sites and cohorts only: Blood sample for RO and PBMC isolation (only on Cycles 1 and 2)
 - Blood sample for PBMC isolation when 'Blood sample for RO and PBMC' is not collected (only in Cycles 1 and 2)
 - sCLEVER-1 RO sample (Cycles 1, 2 and 3)

- OxLDL (only in Cycles 1, 2, 3, and 4)
- Flow cytometry (TBNK cells, CD127 FOXP3 Assay and PD-1 T-Helper Assay) (only in Cycles 1, 2, 3 and 4)
- Cytokine and chemokine panel (only in Cycles 1, 2, 3 and 4)
- Circulating tumour deoxyribonucleic acid (ctDNA) requires genetic consent (only in Cycles 1, 2 and 3)
- Serum or urine pregnancy test (women of child-bearing potential only)
- Imaging
 - MRI/CT (The same imaging method (CT, MRI) per subject must be used throughout the trial. The first scan (C1) must be less than 6 weeks old prior the first dose (routine diagnostic image can be used). Cycles 1, 4, 7, 10, and every third cycle thereafter, up to one year. The images have to be taken as close as possible (\pm 10 days) to the initial schedule even if there are missed IMP doses. If the treatment extends beyond one year, 18- (\pm 1 month) and 24- (\pm 1 month) month images from the first dose are mandatory to take if not routinely taken at these timepoints.
- AE assessment; photographs to document visible AEs should be considered
- Concomitant medications and interventional procedures (including herbal products)

8.4.3 Parameters Collected during Pre-Dose Evaluation in Part III

In Part III the pre-dose assessment is done in every cycle for the 1 -year treatment period if not otherwise stated. Pre-Dose assessments maybe taken also up to three days before the Day 1 in each cycle. See also [Table 3](#) and the Laboratory Manual.

- Height (only in Cycle 1)
- Weight
- Vital signs (blood pressure, heart rate, body temperature and respiratory rate).
- A targeted physical examination covering the major body systems (e.g. general appearance, head [ear, nose and throat], cardiovascular, eyes, respiratory, abdomen, urogenital, musculoskeletal, neurological, lymph nodes and skin)
- ECG (only in Cycle 5; the ECG must be performed also always if clinically indicated)
- ECOG performance status
- PK sampling for population PK
 - For subjects with odd trial numbers (group A) at Cycle 1
 - For subjects with even trial numbers (group B) at Cycle 4
- Subjects with odd trial numbers (group A) only in Cycle 1.
- Subjects with even trial numbers (group B) only in Cycle 4.
- ADA sampling is done only in Cycles 1, 2, 5, 8 and every third cycle thereafter, or if clinically indicated.
- Blood samples
 - CBC
 - CMP
 - Endocrine panel (cortisol, lipase, pancreas-specific amylase, thyroid stimulating hormone, PTH, free thyroxine (T4), free triiodothyronine (T3), troponin)
 - Hepatitis B and C virus (quantitative assessment in Cycles 1, 2, 4 and 6 if tested initially positive)
 - LDH
 - LDL Cholesterol
 - AFP (HCC subjects)

- CRP
- CA-125 (OC subjects)
- CA19-9 (PDAC, gallbladder cancer, cholangiocarcinoma, gastric adenocarcinoma subjects)
- CEA (CRC, ER+ BC, gastric adenocarcinoma subjects)
- CA-15-3 (ER+ BC subjects)
- Research blood samples
 - OxLDL (only in Cycles 1, 2, 3 and 4)
 - Flow cytometry (TBNK cells, CD127 FOXP3 Assay and PD-1 T-Helper Assay) (only in Cycles 1 and 2)
 - Cytokine and chemokine panel (only in Cycles 1 and 2)
 - Blood sample for PBMC isolation (only in Cycles 1 and 4)
 - ctDNA requires genetic consent (only in Cycles 1, 2 and 3)
- Serum or urine pregnancy test (women of child-bearing potential only)
- Tumour Imaging
 - MRI/CT (The same imaging method (CT, MRI) per subject must be used throughout the trial. The first scan (C1) must be less than 6 weeks old prior the first dose (routine diagnostic image can be used). Cycles 1, 4, 7, 10, and every third cycle thereafter, up to one year. The images have to be taken as close as possible (\pm 10 days) to the initial schedule even if there are missed IMP doses. If the treatment extends beyond one year, 18- (\pm 1 month) and 24- (\pm 1 month) month images from the first dose are mandatory to take if not routinely taken at these timepoints)
- AE assessment; photographs to document visible Aes should be considered
- Concomitant medications and interventional procedures (including herbal products)

8.4.4 Samples Collected and Parameters Analysed during and after IMP Administration in Part I

During or after the IMP infusion, parameters for safety and blood samples are collected as follows (see also [Table 1](#) and the Laboratory Manual):

- Vital signs (blood pressure, heart rate, body temperature and respiratory rate)
 - Cycles 1-3: During infusion, 3 additional readings e.g., every 20 minutes for 1 hour. However, the third additional measurement should be performed after the IMP infusion has completed; therefore, if the infusion lasts more than 1 hour, then the third additional measurement may be more than 20 minutes after the second additional measurement. For the subsequent infusions vital signs are to be measured only before and after IMP infusion.
 - in Cycle 1 at 5 hours (+/- 2 hours) after IMP infusion completion
- PK sampling (only in Cycles 1, 2 and 4)
 - 0 h after all IMP has been administered, 1 h (+/- 5 mins), 5 h (+/- 30 mins), D2 (+/- 4 h), D3 (+/- 4 h) D4 (+/- 4 h), D5 (+/- 8 h), and D8 (+/- 24 h) after IMP administration
- Tumour biopsy (only in Cycle 2)
 - Should be obtained within 10 days after the IMP administration. See the Laboratory Manual for sample procurement and handling procedures.
- ECG (only in Cycles 1 and 4)
 - 0 h after the infusion and PK sampling
- Blood samples (only in Cycle 1)
 - CBC on D5 (+/- 4 h)
 - CMP on D5 (+/- 4 h)

- Research blood samples
 - Receptor occupancy and monocytes (RO assay) (only in Cycles 1 and 2) D2 (+/- 4 h), D8 (+/- 24 h) and D15 (+/- 24 h)
 - Flow cytometry (TBNK cells and CD127 FOXP3 Assay) (only in Cycles 1 and 2) D2 (+/- 4 h), D8 (+/- 24 h) and D15 (+/- 24 h)
 - Cytokine and chemokine panel (only in Cycles 1 and 2) D8 (+/-24 h) and D15 (+/- 24 h)
 - Blood sample for PBMC isolation (only in Cycle 1) D5 (+/- 4 h)
- AE assessment. NOTE: AE assessments should be conducted each time the subject is visiting the hospital. Photographs to document visible Aes should be considered.

8.4.5 Samples Collected and Parameters Analysed during and after IMP Administration in Part II

During or after the IMP infusion, parameters for safety and blood samples are collected as follows (see also [Table 2](#) and the Laboratory Manual):

- Vital signs (blood pressure, heart rate, body temperature and respiratory rate)
 - Cycles 1-3: 20 minutes after the start of the infusion, 40 minutes after the start of the infusion and at 1 h after the start of the infusion or at the end of the infusion (immediately after flushing the line), whichever occurs later. For the subsequent infusions vital signs are to be measured only before and after IMP infusion.
 - in Cycle 1 at 5 hours (+/- 2 hours) after IMP infusion completion
- PK sampling (only in Cycles 1 and 2)
 - 0 h after all IMP has been administered, 1 h (+/- 5 mins), 5 h (+/- 30 mins), D2 (+/- 4 h), D3 (+/- 4 h) D4 (+/- 4 h), D5 (+/- 8 h), and D8 (+/- 24 h)
- Tumour biopsy (only in Cycle 2 and if any new lesions)
 - Cycle 2 biopsy should be obtained within 10 days after the IMP administration. See the Laboratory Manual for sample procurement and handling procedures.
 - Biopsy from new lesions is recommended if assessed feasible by the investigator considering the location of the lesions and condition of the subject.
- ECG (only in Cycles 1 and 4)
 - 0 h after the infusion and PK sampling
- Blood samples
 - CBC on D5 (+/- 8 h) (only in Cycle 1)
 - CMP on D5 (+/- 8 h) (only in Cycle 1)
 - CMP on D8 (+/- 24h) (only in Cycles 2 and 3)
- Research blood samples
 - At selected sites and cohorts only: Blood sample for RO and PBMC isolation (only in Cycle 1) D2 (+/- 4 h), D8 (+/- 24 h) and D15 (+/- 24 h)
 - Blood sample for PBMC isolation when 'Blood sample for RO and PBMC' is not collected (only in Cycle 1) D2 (+/- 4 h), D8 (+/- 24 h) and D15 (+/- 24 h)
 - sCLEVER-1 RO sample (only in Cycles 1 and 2) D2 (+/- 4 h), D8 (+/- 24 h) and D15 (+/- 24 h)
 - Flow cytometry (TBNK cells, CD127 FOXP3 Assay and PD-1 T-Helper Assay) (only on Cycles 1 and 2) D2 (+/- 4 h), D8 (+/- 24 h) and D15 (+/- 24 h)
 - Cytokine and chemokine panel (only on Cycles 1 and 2) D8 (+/-24 h) and D15 (+/- 24 h)
- AE assessment. NOTE: AE assessments should be conducted each time the subject is visiting the hospital. Photographs to document visible AEs should be considered.

8.4.6 Samples Collected and Parameters Analysed during and after IMP Administration in Part III

- During or after the IMP infusion, parameters and blood samples are collected as follows (see also [Table 3](#)):
 - Vital signs (blood pressure, heart rate, body temperature and respiratory rate)
 - Cycles 1-3: 20 minutes after the start of the infusion, 40 minutes after the start of the infusion and at 1 h after the start of the infusion or at the end of the infusion (immediately after flushing the line), whichever occurs later. For the subsequent infusions vital signs are to be measured only before and after IMP infusion.
- PK sampling for population PK
 - For subjects with odd trial numbers (group A) PK sampling will be at Cycle 1 Day 2 (+/- 2 h), at Cycle 1 Day 5 (+/- 24 h), at Cycle 2 Day 1 four hours (+/- 2 h) after all IMP has been administered, and at Cycle 4 D3 (+/- 24 h)
 - For subjects with even trial numbers (group B) PK sampling will be at Cycle 1 Day 1 four hours (+/- 2 h) after all IMP has been administered, at Cycle 1 Day 3 (+/- 24 h), at Cycle 2 Day 2 (+/- 2 h), and at Cycle 4 Day 5 (+/- 24 h)
- Tumour biopsy (only in Cycle 2 and if any new lesions)
 - Cycle 2 biopsy should be obtained within 10 days after the IMP administration. See the Laboratory Manual for sample procurement and handling procedures.
 - Biopsy from new lesions is recommended if assessed feasible by the investigator considering the location of the lesions and condition of the subject.
- Blood samples
 - CMP on D5 (+/- 8 h) (only in Cycle 1)
 - CMP on D8 (+/- 24h) (only in Cycles 2 and 3)
- Research blood samples (Cycle 1 only)
 - Flow cytometry (TBNK cells, CD127 FOXP3 Assay and PD-1 T-Helper Assay) on D8 (+/- 24 h) and D15 (+/- 24 h)
 - Cytokine and chemokine panel on D8 (+/- 24 h) and D15 (+/- 24 h)
 - Blood sample for PBMC isolation on D8 (+/- 24 h)
- AE assessment. NOTE: AE assessments should be conducted each time the subject is visiting the hospital. Photographs to document visible AEs should be considered.

8.4.7 Tumour Assessment

Tumour assessment is done at the treating site according to RECIST 1.1 (Eisenhauer et al. 2009; Appendix 1 - RECIST Criteria) and Immune-related response criteria ([Appendix 2](#) - Immune-related Response Criteria). MRI/CT (chest, abdomen and pelvis) slice thickness must be 5 mm or less. In case of suspicion of pseudoprogression and subjective stable disease (no clinical deterioration) a second tumour evaluation should be carried out at least 4 weeks after the first response evaluation even if the subject has been deemed to discontinue from the study. For evaluable subjects, the response will be reported in each cohort as the numbers of subjects who have CR, PR, SD, or progressive disease as well as irCR, irPR, irSD, or ir-progressive disease.

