¹⁷ Predose assessment in Cycles 1, 2, 3 and 4. Post IMP administration timepoints in Cycles 1 and 2 D2 (+/- 4 h), D8 (+/- 24h) and D15 (+/- 24 h)

¹⁸ Predose assessment in Cycles 1, 2, 3 and 4. Post IMP administration timepoints in Cycles 1 and 2 D8 (+/-24 h) and D15 (+/- 24 h)

¹⁹ First tumour biopsy must be less than 6 months old from the date of consent or taken during the screening period. In addition, an archival block may be used if needed; the biopsy in Cycle 2 within 10 days after the IMP administration. Biopsy from new lesions is recommended if assessed feasible by the investigator considering the location of the lesions and condition of the subject.

²⁰ The same imaging method (CT, MRI) per subject must be used throughout the trial. First scan (C1) must be less than 6 weeks prior the first dose (routine diagnostic image can be used); the scans in other cycles within +/- 10 days from the IMP administration

²¹ Cycles 1, 4, 7, 10, and every third cycle thereafter, up to one year. If the treatment extends beyond one year, 18- (\pm 1 month) and 24- (\pm 1 month) month images are mandatory to take if not routinely taken at these timepoints. In addition to the imaging time-points specified here, also any other imaging performed by the site will also be collected.

²² Brain imaging (CT) for exclusion of CNS metastasis. Routine diagnostic image (CT/MRI) can be used if available. The brain scan within six weeks prior to the 1st dose is acceptable.

²³ First three subjects testing new doses or dosing frequencies in Part II should be closely monitored for safety for the first 24 h after the first IMP infusion and for a minimum of 6 h after the second IMP infusion at the trial site hospital. Other subjects in Part II will be monitored for a minimum of 6 h after the first IMP infusion. After Cycle 1 all subjects should be observed for a minimum of 2 h after the IMP infusions. In any part of the trial, post-dose observation will be longer if deemed appropriate. AE assessment done if visit indicated.

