2.5.9 Anaplastic thyroid cancer

Anaplastic thyroid cancer (ATC) is an aggressive form of thyroid cancer with a mortality approaching 100%. It is rare and accounts for about 2% of all thyroid cancers. Patients are diagnosed based on clinical symptoms. Patients with the disease present with extensive local invasion. Distant metastases are found at initial disease presentation in 15% to 50% of patients. No curative therapy exists for ATC. Surgery, external beam radiotherapy or chemoradiotherapy are options for local disease control. For metastatic disease, systemic therapies include combinations of paclitaxel and carboplatin or docetaxel and doxorubicin. Paclitaxel or doxorubicin may also be used alone. However, the

median survival from ATC diagnosis is about five months. The one-year survival rate is about 20% (Smallridge et al. 2012).

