5.1 Inclusion and Exclusion Criteria

5.1.1 Inclusion Criteria

Subjects must meet all of the following inclusion criteria to be eligible for participation in the clinical trial:

- 1) Written Informed Consent
- 2) Aged \geq 18 years male or female
- 3) Tumour sample should be collected during screening period. If a recent tumour biopsy obtained within six months before the date of consent is available (or older, as agreed on a case by case basis with the sponsor), that may be used. At the discretion of the sponsor, the tumour sample may be optional for certain subjects in Part III
- 4) Life expectancy $>$ 12 weeks
- 5) Histologically confirmed advanced (inoperable or metastatic) malignancies in which (according to the view of the investigator) no curative, effective or suitable treatment options exist.
 - Hepatocellular carcinoma
 - Gallbladder cancer or intra- or extrahepatic cholangiocarcinoma
 - Colorectal adenocarcinoma
 - Serous poorly differentiated (Grade 3) ovarian adenocarcinoma or undifferentiated ovarian cancer
 - Pancreatic ductal adenocarcinoma
 - Immunotherapy (IO) resistant cutaneous melanoma (progression during programmed cell death protein-1 (PD-1)/programmed cell death ligand-1 (PD-L1) or CTLA-4 antibody therapy)
 - Uveal melanoma in Parts II and III
 - Gastric adenocarcinoma (including adenocarcinoma of the distal esophagus / GE junction) in Parts II and III
 - ER+ breast cancer in Parts II and III
 - Anaplastic thyroid cancer in Parts II and III
- 6) Eastern Cooperative Oncology Group (ECOG) performance status 0 or 1
- 7) Measurable disease in Parts II and III
- 8) Adequate bone marrow, liver and kidney function defined as

Blood white blood cell \geq lower limit of normal

Blood neutrophil count $\geq 1 \times 10^9/L$

Blood platelet count $\geq 100 \times 10^9/L$, for HCC $\geq 50 \times 10^9/L$

Blood haemoglobin $\geq 9.0 \text{ g/dL}$

Creatinine clearance $> 40 \text{ mL/min}$ calculated by Cockcroft-Gault formula

AST $\leq 3 \times \text{ULN}$ ($\leq 5 \times \text{ULN}$ when HCC or hepatic metastases are present)

ALT $\leq 3 \times \text{ULN}$ ($\leq 5 \times \text{ULN}$ when HCC or hepatic metastases present)

Bilirubin $\leq 1.5 \times \text{ULN}$

Albumin $\geq 3.0 \text{ g/dL}$

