irPR	Decrease of $\geq 30\%$ in TMTB relative to baseline. Confirmation by two consecutive observations not less than 4 weeks apart is required.
irProgressive disease	Minimum 20% increase and minimum 5 mm absolute increase in TMTB compared to nadir. Confirmation by two consecutive observations not less than 4 weeks apart is required.
irSD	No irCR or irPR in the absence of irProgressive disease.

Notes:

1. To achieve "unequivocal progression" on the basis of the non-target disease, there must be an overall level of substantial worsening in non-target disease and symptoms such that, even in presence of irSD or irPR in target disease, the overall tumour burden has increased sufficiently to merit discontinuation of therapy.

B. Evaluation of Non-Target Lesions

Response Category	Description
irCR	Disappearance of all non-target lesions
irProgressive disease	Unequivocal progression of non-target lesions

C. Evaluation of Best Overall Response

The best overall response is the best response recorded from the start of treatment until disease progression. In general, the patient's best response assignment will depend on the achievement of both measurement and confirmation criteria.

D. Overall Responses for All Possible Combinations of Tumour Responses in Target and Non-Target Lesions with or without the Appearance of New Lesions

Target Lesions	Non-target Lesions	Overall Response
irCR	irCR	irCR
irCR	non-irProgressive disease	irPR
irPR	irCR	irPR
irPR	non-irProgressive disease	irPR
irSD	non-irProgressive disease	irSD
Any	irProgressive disease	irProgressive disease

Patients with a global deterioration of health status requiring discontinuation of treatment without objective evidence of disease progression at that time should be classified as having "symptomatic deterioration." Every effort should be made to document the objective disease progression, even after discontinuation of treatment.

Frequency of Tumour Re-evaluations

For the trial, clinical response rate, disease control rate (CR+PR+SD), PFS and duration of response will be evaluated by CT or MRI scan of the abdomen at baseline. Repeat imaging must be performed with the same method and will be performed according to schedule of assessment.

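### The scan field for the primary response endpoints is stated in two different ways, and neither statement requires the neck for the anaplastic thyroid cancer cohort

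*Protocol*

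**What the plan says.** Two current parts of the protocol name an anatomical field for tumour imaging.

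- Section 8.4.7 (Tumour Assessment): "MRI/CT (chest, abdomen and pelvis) slice thickness must be 5 mm or less".
- Appendix 2, under the frequency of re-evaluations, as an instruction for this trial covering response rate, disease control rate and more: "PFS and duration of response will be evaluated by CT or MRI scan of the abdomen at baseline". It continues: "Repeat imaging must be performed with the same method and will be performed according to schedule of assessment".

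The schedule tables in section 1.3 and the pre-dose lists in 8.4.1 to 8.4.3 give modality and timing, but no field. The only scheduled imaging above the chest is at screening: "Brain imaging (CT) for exclusion of CNS metastasis".

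The inclusion criteria (5.1.1) list "Anaplastic thyroid cancer in Parts II and III". Of this disease, section 2.5.9 says "Patients with the disease present with extensive local invasion".

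ORR, CBR and irORR, the Part II and III response endpoints, are read from these images. CBR counts stable disease. Protocol 15.7 and the Part II SAP (sections 7 and 12.1) allow a cohort to expand when at least one of ten subjects shows clinical benefit, and SAP 12.1 accepts that benefit at Cycle 4 or Cycle 7.

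**The concern.** A site cannot follow both statements exactly. One that follows Appendix 2 has no chest baseline. Lung or mediastinal disease found later may then be called a new lesion, which scores as progression although it may have been there from the start. If the chest is never scanned, the disease is missed. The first error lowers CBR and the second raises it, so the bias has no fixed direction and may vary between sites. Reading is done at the treating site.

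For anaplastic thyroid cancer, a site can comply with either statement and never image the neck, where the primary tumour lies. If the target lesions are in the trunk and the local disease is not imaged, local growth can go unrecorded and the subject can be scored as stable. That counts towards CBR, and one such subject is enough to reach the expansion threshold.

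**Working it through.** **1. The two statements side by side**

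| | Section 8.4.7 | Appendix 2 |
|---|---|---|
| Field | chest, abdomen, pelvis | abdomen |
| Context | slice-thickness rule, in a parenthesis | trial-specific sentence on how the endpoints are evaluated |
| Neck required | no | no |
| Repeat scans | field not restated | same method, no wider field |

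Section 8.4.7 itself sends the reader to both appendices, so Appendix 2 is operative text.

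**2. When a false stable disease can arise (Appendix 1 rules)**

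- Neck lesion is a target and is not assessed: overall response is not evaluable, not stable.
- Neck lesion is a target measured by caliper: it is followed and can show progression.
- Neck lesion is a recorded non-target and is followed: unequivocal progression gives overall progression.
- Targets lie inside the scanned field, and the neck disease is not imaged or is recorded only as non-target without follow-up imaging: progression there can be missed and the overall response can be stable.

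Only the last case produces the error.

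**3. The plan's own decision rule, reproduced**

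Inputs from protocol 15.7: null 5%, alternative 20%, one-sided alpha 0.05, power 0.80, 10 then 29 subjects, continue with at least 1/10, succeed with at least 4/29.

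P(success | p) = Σ over x = 1 to 10 of P(X₁ = x) · P(X₂ ≥ 4 − x), with X₁ ~ Bin(10, p) and X₂ ~ Bin(19, p).

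- p = 0.05: 0.0468 (type I error)
- p = 0.20: 0.8011 (power)
- Stopping after ten at p = 0.05: 0.95¹⁰ = 0.599; expected size 10 + 19 × (1 − 0.599) = 17.6

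The stated design reproduces.

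**4. Sensitivity to misclassification (assumption)**

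Let m be the share of subjects without true benefit who are scored stable because their progression lies outside the scanned field. The documents give no value for m. With the true CBR at the plan's null of 5%, the apparent CBR is p = 0.05 + 0.95m. The chance of passing the first stage is 1 − (1 − p)¹⁰; the final column uses the formula in step 3 and assumes the same m in Part III.

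| m (assumed) | apparent p | at least 1/10 | at least 4/29 |
|---|---|---|---|
| 0 | 0.050 | 40.1% | 4.7% |
| 2% | 0.069 | 51.1% | 11.8% |
| 5% | 0.0975 | 64.2% | 27.4% |
| 10% | 0.145 | 79.1% | 56.2% |
| 20% | 0.240 | 93.6% | 89.7% |

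The table shows how little error the rule tolerates. It does not estimate how much error occurs.

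**The case against.** The case against is substantial.

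- The field in 8.4.7 sits inside a thickness requirement and does not exclude other regions. A careful site would image known disease. This stands as a description of likely practice, but it does not make the scans uniform or resolve the conflict with Appendix 2.
- Appendix 1 accepts lesions of at least 10 mm by caliper, asks for targets that represent every involved organ, and has all other disease sites recorded and followed. The per-cycle examination in 8.4.2 covers the head and lymph nodes. These safeguards stand and narrow the concern. They fix no repeatable scan field, and calipers do not reach deep invasion.
- For baseline lesions Appendix 2 refers back to RECIST 1.1, so its abdomen sentence is probably a drafting slip. That is plausible, and it is a reason to correct the sentence.
- Meeting 1/10 only permits expansion. Protocol section 4 says weak signals need not be advanced. This stands.
- Part II SAP section 2 reports that the original cohorts (n=120) have finished treatment. Section 9.2 gives n=110 without anaplastic thyroid cancer, so that cohort's ten subjects (120 − 110) are among them. New wording cannot change their scans. This stands, and affects the fix.

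A reader might infer the size of the problem from section 2.5.9: "Distant metastases are found at initial disease presentation in 15% to 50% of patients", hence 50% to 85% without distant disease (100% − 50%; 100% − 15%). The documents do not support that use. The figure describes first presentation, not this trial's population. Criterion 7 also requires measurable disease, so a subject with neck-only disease is either ineligible or already has a measured neck lesion. The false-stable route needs a target inside the scanned field, which mostly means subjects with disease elsewhere.

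**Conclusion.** The inconsistency is real, and so is the absence of any neck requirement. Both feed ORR, CBR, irORR and PFS. The consequence is limited and conditional: progression outside the scanned field can be missed when the targets lie inside it, and chest disease can be miscalled new or missed when there is no chest baseline.

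A reader might also infer that unimaged neck disease can never be a target, that its growth can never count as progression, or that any subject with local progression will be scored stable. Appendix 1 contradicts each of these in the cases set out in the working.

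The size cannot be derived from the documents. What can be said is that one wrongly stable subject in a cohort of ten with no true benefit reaches the expansion threshold, and that the assumed values of m show the rule is sensitive to small error rates. The conclusion assumes that sites may follow the written field literally. It should be fixed, but it does not undermine the design as a whole.

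**What to change.** **Protocol.** Reconcile Appendix 2 with section 8.4.7 so that both state one field: chest, abdomen and pelvis, plus the neck for anaplastic thyroid cancer and any other known disease site, with the same field at baseline and at every follow-up scan.

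**Subjects already treated.** For the anaplastic thyroid cohort, list the field actually scanned for each subject at baseline and follow-up, and show it when the cohort's CBR is reported.

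**Cost.** A wording change, a short listing, and a slightly longer scan session in one cohort. No extra visit is needed. The amendment helps later Part II cohorts and Part III; the listing is the only remedy for completed scans.
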